Synopsis Study Portocol (DigesT trial)	
Study title	Impact of Dietary Intervention on tumor immunity: the DigesT trial
Study Sponsor	Fondazione IRCCS Istituto Nazionale dei Tumori di Milano
Coordinating Center	Fondazione IRCCS Istituto Nazionale dei Tumori di Milano
Background	
Metabolic reprogramming is a hallmark of cancer. Human cancers are able to use blood metabolites and growth factors to fulfill their energetic and anabolic requirements. In particular, blood glucose stimulates aerobic glycolysis in cancer cells, thus leading to the production of ATP units and precursors of amino acid and nucleotide biosynthesis. Moreover, circulating growth factors, such as insulin and insulin-like growth factor 1 (IGF-1), can induce the activation of the PI3K/AKT/mTOR pathway, which in turn stimulates protein, fatty acid and cholesterol biosynthesis in cancer cells. Not only systemic metabolism can sustain cancer cell growth and proliferation; it also impacts on the proliferation and activation status of circulating immune cells, including protumor and antitumor immune cells. For example, circulating IGF-1 can inhibit the activation and memory functions of T lymphocytes, while the proliferation of myeloid derived suppressive cells (MDSCs) is stimulated by circulating glucose and eicosapentanoic acid. Different metabolic blood profiles could exert stimulatory or inhibitory effects on specific immune cell populations, thus setting a specific balance between protumor and antitumor activities.

Hypothesis/Rationale	
Modifying systemic metabolism could affect cancer cell metabolism and the activation of specific immune cell populations. In recent years, a plant-based, calorie-restricted, low-carbohydrate, low-protein diet, also known as the Fasting Mimicking Diet (FMD) has been proposed as a potential anticancer dietary intervention. The FMD is safe when administered cyclically (every 21-28 days) to healthy volunteers, and is capable of significantly reducing the concentration of blood glucose, insulin and IGF-1, while increasing levels of IGFBPs and ketone bodies. The FMD has been shown to inhibit the in vivo growth of several tumor models,

	
including breast cancer and melanoma mice models. The anticancer effects of the FMD are likely mediated by two concomitant mechanisms: 1) one direct anticancer effect that is mediated by the inhibition of energy production and anabolic pathways, such as protein and fatty acid synthesis, in cancer cells; 2) one indirect effect that is mediated by the activation of antitumor immunity, with the result of enhanced tumor infiltration by cytotoxic T-lymphocytes and reduced infiltration by immunosuppressive populations. Both effects derive from changes in blood metabolites, which can impact on the growth and proliferation of both cancer and immune cells. According to the currently accepted model, the anticancer and immunomodulatory effects of the FMD mostly derive from the reduction of circulating glucose, insulin and IGF-1 levels, and a parallel increase of ketone body and IGF-1 binding protein concentration. However, based on recent discoveries, FMD-mediated changes in many other metabolites, such as specific amino acids (e.g. tryptophan, arginine, methionine, glutamine, serine) or fatty acids (e.g. arachidonic acid, eicosapentanoic acid), could contribute to the cell-autonomous or immune-mediated anticancer effects of the FMD.
 
While the study of the effects of the FMD in combination with standard treatments (e.g. chemotherapy, molecular targeted therapy) in advanced cancers represents the final objective of the ongoing studies, fully uncovering the metabolic and immunological effects of the FMD alone is essential to design future combination studies. From this perspective, the pre- ad post-operative clinical settings in cancer patients who are not candidate to other medical treatments represent an ideal context to assess the effects of the FMD without other confounding factors.

Objectives and corresponding endpoints	
Primary objective and corresponding endpoint:
 
To evaluate the short-term and long-term efficacy of the FMD to down-modulate protumor peripheral blood mononuclear cells (PBMCs), including myeloid-derived suppressive cells (MDSCs), and to up-regulate antitumor cells, such as activated T cells and NK cells. Short-term modifications refer to changes assessed the day of FMD discontinuation compared to the day of FMD initiation. Long-term modifications refer to changes detected the day of surgery or 30 days after surgery compared to the day of FMD initiation.
 
Secondary objectives and endpoints:
 
1. To assess by single-cell “mass cytometry” (CyTOF) phenotypic and functional modifications in PBMCs and tumor-infiltrating lymphocytes during the FMD.2. To perform transcriptional and miRNA profiling in PBMCs, tumor cells (Cohort A) and immune cell populations inside lymph nodes (Cohort B).3. To assess changes in the expression of metabolic genes, such as those involved in glycolysis,

	
trycarboxylic acid cycle, amino acid synthesis, fatty acid and cholesterol de novo biosynthesis in PBMCs.
 
4. To assess FMD-induced changes in blood (glucose, triglycerides, fatty acids, cholesterol, amino acids) and urine (ketone bodies) metabolic parameters.5. To assess FMD-induced changes in plasmatic growth factors, such as insulin, IGF-1, vascular endothelial growth factor (VEGF), platelet-derived growth factor (PDGF), fibroblast growth factor (FGF), IGF1 binding proteins 1 and 3 (IGFBP-1 and IGFBP-3).6. To evaluate by immunohistochemistry (IHC) or multiple immunofluorescence (IF) quantitative and qualitative changes in tumor immune cell infiltrate, including myeloid, T and NK cell markers, by comparing the diagnostic biopsy specimen with the tumor specimen after surgical removal of the primary tumor (Cohort A).7. To assess changes in tumor proliferation index (Ki67), apoptosis (caspase 3 by IHC), autophagy (LC3), glycolysis (Glut1), tumor grade and immunohistochemical expression of estrogen and/progesterone receptor and HER2 oncoprotein in breast cancer patients (Cohort A).8. To evaluate quantitative and qualitative changes in immune cell suspensions from lymph nodes of melanoma patients undergoing one FMD cycle before lymph node dissection (Cohort B).9. To evaluate changes in DNA methylation profiles in tumor and lymph node tissues from patients undergoing the FMD before surgery (Cohorts A and B).10. To assess modifications in gut microbiota community composition, as detected by 16S rRNA gene sequencing and shotgun metagenome sequencing of patient stool samples before and after the FMD.11. To evaluate short-term and long-term modification of systemic nutritional parameters (serum albumin, transferrin, pre-albumin, retinol-binding protein and lymphocyte counts) after one FMD cycle for patients in cohort A and B and after 4 FMD cycles for patients in Cohort C.12. To evaluate changes induced by the experimental treatment in the hematologic profile (white blood cell counts, lymphocyte counts, hemoglobin concentration, platelet counts, red blood cell counts).13. To investigate patient compliance to the diet, as assessed through the analysis of dietary diaries and measured by counting minor and major deviations from the prescribed FMD regimen.14. To assess the tolerability of the prescribed FMD regimen, including adverse events and serious adverse events occurring during the FMD and after its discontinuation.15. To correlate FMD-induced changes in serum metabolites with changes in PBMCs, their activation status, as well as with tumor cell and immune infiltrate characteristics.
--	--

	
Inclusion criteria
 
Patients eligible for inclusion in this study have to meet all of the following criteria:
 
1. Age \geq 18 and \leq 75 years.
 
2. Evidence of a personally signed and dated informed consent document (ICD) indicating that the patient has been informed of all pertinent aspects of the study before enrollment and FMD prescription.
 
3. Willingness and ability to comply with the FMD protocol, the scheduled visits, treatment plans, laboratory tests and other procedures.
 
4. Histologically confirmed diagnosis of invasive breast cancer candidate to curative surgery (Cohort A), or resected malignant melanoma requiring dissection of the regional lymph node basin for sentinel lymph node involvement (Cohort B), or malignant melanoma treated with curative surgery (including, in case, lymph node removal and lymph node dissection) (Cohort C). For breast cancer patients, any biological subgroup (including estrogen receptor-positive, HER2-positive, triple-negative breast cancer) will be admitted; HER2-positive tumors will be defined on the basis of an IHC score of 3, or a score of 2 with ISH evaluation indicative of gene amplification.
 
5. Availability of archival FFPE tissue blocks of primary breast cancer (Cohort A) or melanoma (Cohort B, Cohort C).
 
6. Presence of an Eastern Cooperative Oncology Group (ECOG) performance status 0 or 1.
 
7. Presence of adequate bone marrow and organ function as defined by the following laboratory values:
 
- ANC $\geq 1.5 \times 10^9/l$- platelets $\geq 100 \times 10^9/l$- hemoglobin $\geq 9.0 \text{ g/dl}$- calcium (corrected for serum albumin) within normal limits or \leq grade 1 according to NCI-CTCAE version 4.03 if not clinically significant- potassium within the normal limits, or corrected with supplements- creatinine $< 1.5 \text{ ULN}$- blood uric acid $< 10 \text{ mg/dl}$- ALT and AST $\leq 2.5 \times \text{ULN}$- total bilirubin $< \text{ULN}$ except for patients with Gilbert syndrome who may only be
--	---

	
included in the total bilirubin is < 3.0 x ULN or direct bilirubin < 1.5 x ULN
 
- Albumin > 3 g/dL 
8. Fasting glucose ≤ 200 mg/dL.9. Total Cholesterol ≤ 300 mg/dL.10. Triglycerides ≤ 300 mg/dL.11. Female patients of childbearing potential must agree to sexual abstinence or to use two highly effective method of contraception throughout the study and for at least 30 days after the end of the FMD. Abstinence is only acceptable if it is in line with the preferred and usual lifestyle of the patient. Examples of contraceptive methods with a failure rate of < 1% per year include tubal ligation, male sterilization, hormonal implants, established, proper use of combined oral or injected hormonal contraceptives, and certain intrauterine devices. Alternatively, two methods (e.g., two barrier methods such as a condom and a cervical cap) may be combined to achieve a failure rate of < 1% per year. Barrier methods must always be supplemented with the use of a spermicide. A patient is of childbearing potential if, in the opinion of the Investigator, she is biologically capable of having children and is sexually active. Female patients are not of childbearing potential if they meet at least one of the following criteria:
• Have undergone a documented hysterectomy and/or bilateral oophorectomy• Have medically confirmed ovarian failure• Achieved post-menopausal status, defined as: (\geq 12 months of non-therapy-induced amenorrhea) or surgically sterile (absence of ovaries) and have a serum FSH level within the laboratory's reference range for postmenopausal females.
	
5.3 Exclusion criteria
 
Patients eligible for this study must not meet any of the following criteria:
 
1. Prior systemic treatment for breast cancer or melanoma.2. Diagnosis of a concurrent malignancy other than breast cancer or melanoma, or malignancy other than breast cancer or melanoma diagnosed within 5 years of treatment enrollment, with the exception of adequately treated, basal or squamous cell carcinoma, non-melanomatous skin cancer or curatively resected cervical cancer.3. Body Mass Index (BMI) < 20 Kg/m².

	
4. Anamnesis of alcohol abuse.5. Unintentional weight loss $\geq 5\%$ in the last three months, unless the patient has a BMI $> 25 \text{ Kg/m}^2$ at study enrollment. Intentional weight loss is permitted if $< 10\%$ in the last three months and patient BMI is $> 22 \text{ kg/m}^2$.6. Severe heart, liver, pulmonary, kidney comorbidities.7. Current status of pregnancy or lactation, where pregnancy is defined as the state of a female after conception and until the termination of gestation, confirmed by a positive hCG laboratory test ($> 5 \text{ mIU/mL}$).8. Active HBV or HCV infection.9. Severe infections within 4 weeks prior to FMD initiation, including, but not limited to, hospitalization for complications of infection, bacteremia, or severe pneumonia.10. Active autoimmune diseases that require systemic treatment (i.e. with use of disease modifying agents, corticosteroids or immunosuppressive drugs).11. History of recent diagnosis of hypothyroidism for which replacement therapy (eg., thyroxine) and blood endocrine profile are not stabilized yet.12. Established diagnosis of diabetes mellitus type I or diabetes mellitus type II that requires pharmacological treatment (including, but not limited to, insulin, insulin secretagogues and metformin).13. Severe impairment of the gastrointestinal (GI) function or GI disease that may alter the digestion and absorption of nutrients during the re-feeding phase (e.g. active ulcerative diseases of the stomach or intestine, uncontrolled nausea, vomiting, diarrhea, malabsorption syndrome, or small bowel resection).14. Known history of Human Immunodeficiency Virus (HIV) infection.15. Clinically significant heart disease and/or recent cardiac events including:
a) history of angina pectoris, coronary artery bypass graft (CABG), symptomatic pericarditis, or myocardial infarction within 12 months prior to the start of study treatment;b) history of documented congestive heart failure (NYHA III-IV);c) documented cardiomyopathy.16. History of cardiac arrhythmias, (e.g. ventricular tachycardia, chronic atrial fibrillation), complete left bundle branch block, high grade AV block (e.g. bifascicular block, Mobitz type II and third degree AV block), supraventricular, nodal arrhythmias, or conduction abnormality in the previous 12 months.17. Uncontrolled hypertension defined by a Systolic Blood Pressure (SBP) $\geq 160 \text{ mmHg}$ and/or Diastolic Blood Pressure (DBP) $\geq 100 \text{ mmHg}$, with or without anti-hypertensive medication.18. Known reduction of left-ventricular ejection fraction (LVEF) to less than 50%, as assessed by multigated radionuclide scintigraphic scan (MUGA) or echocardiography.19. Previous episodes of symptomatic hypotension causing unconsciousness.
--	--

	
20. Baseline fasting plasma glucose ≤ 65 mg/dl.
 
21. Ongoing therapy with systemic corticosteroids, or systemic corticosteroid therapy ≤ 2 weeks before study enrollment, or who have not recovered from side effects of such treatment. The following uses of corticosteroids are permitted: topical applications (e.g. for rash), inhaled sprays (e.g. for obstructive airways diseases), eye drops.
 
22. Any serious medical or psychiatric illness that in the assessment of the investigator renders the patient not suitable for participation in this clinical study.

Study Design and Treatment	
Single-arm, monocentric, prospective study designed to estimate the immunomodulatory and metabolic effects induced by the FMD in breast cancer and melanoma patients.
 
Three different patient cohorts will be enrolled: 1) Cohort A: 40 breast cancer patients candidate to curative surgery without pre-operative systemic treatment. Patients with clinical stages T1N0M0, or those with T1N1M0-T2N0M0 tumors not requiring pre-operative systemic treatment, will be enrolled. Patients with any breast cancer biology, including hormone receptor-positive, HER2-overexpressing and triple-negative cancers, will be included in the study; 2) Cohort B: 40 melanoma patients candidate to lymph node basin dissection after the histological documentation of sentinel lymph node tumor involvement; 3) Cohort C: 20 patients with surgically resected malignant melanoma not candidate to any adjuvant treatment.
 
All patients will be prescribed 5-day low-protein, low-carbohydrate FMD, consisting in a list of allowed foods and quantities to be consumed during each of the five days. Foods or beverages not explicitly included in the prescribed scheme are not permitted. On day 1, the total caloric content of the FMD is of about 700 KCal; on days 2-5, the caloric content is 300 KCal.
 
Patients in Cohort A and B (i.e. those patients receiving the FMD in the pre-operative setting) will receive only one FMD cycle, to be initiated within 15 days from surgery, and to be completed at least 7 days before surgery. Blood, urine and stool samples will be collected just before FMD initiation and at diet completion, to assess FMD-induced effects on systemic immunity and metabolism, as well as the modulatory effects on gut microbiota composition and stool metabolites. Moreover, FMD-induced modifications in the intratumor immune infiltrate and tumor biology (e.g. proliferation index, ER, PgR and Her2 status) will be assessed by comparing diagnostic biopsies with surgical tumor specimens (Cohort A); in Cohort B, the composition of immune cell populations in sentinel lymph node(s) (before the FMD) and in lymph nodes resected at the moment of basin dissection (after the FMD) will be compared as well. Moreover, immune cell suspensions from surgically removed lymph nodes will be obtained from fresh lymph node samples after the FMD to quantify different population subsets, and compared with matched controls of patients with similar characteristics, who were not eligible for enrollment in the trial, or directly refused to be enrolled.


	Patients in Cohort C will receive four consecutive FMD cycles every 28 days. Blood, urine and stool samples will be collected before and after FMD cycles n.1 and n.4, as well as 30 days after completion of 4 FMD cycles, to assess short- and long-term changes in systemic metabolism and immunity.
Duration of the treatment	Enrolled patients will undergo the experimental intervention (namely the FMD) for one cycle (Cohorts A, B) or 4 consecutive cycles (Cohort C). The intervention will be interrupted in the case of unacceptable toxicities, consent withdrawal, patient death or for other reasons at the discretion of the Investigators.
Planned sample size	100 patients (40 in cohort A; 40 in cohort B; 20 in cohort C)
Study period	30 months of enrollment and 6 months of follow up

Statistical methodology	
The main goal of this project is to find systemic, tumor or lymph node immunologic modulation patterns that are significantly modified by the FMD. This assessment will be made on the basis of many indicators belonging to distinct biological systems, while a synthetic criterion for judging treatment effectiveness on this ground is lacking. This situation precludes the possibility to estimate upfront the statistical properties of our study. Nevertheless, the planned sample size in the three patient Cohorts was chosen in the attempt to guarantee study feasibility and patient enrollment within two years from study initiation, while contemporarily providing a sufficient patient number to describe the eventual variability in FMD-induced immunological, metabolic and gut microbiota modifications. The analysis of study results will be based on calculation of descriptive statistics suitable for continuous (mean, median, standard deviation, interquartile range) or categorical (absolute/ relative frequencies) variables. Statistical testing will be preferably based on non-parametric location tests for bivariate comparisons like the Wilcoxon-Mann-Whitney test or the Wilcoxon Signed-Rank Test in case of paired data. Generalized linear models will also be used for a comprehensive analysis of longitudinal data. Finally, robustness of statistical results focusing on single variables will be checked using suitable adjustments for multiple testing, like the Hommel's procedure (1988) for controlling the family wise error rate (FWER). The conventional 5% threshold of statistical significance for two-sided tests will be used throughout.

--------------------------------	--

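### Exclusion 5 waives the 5% limit on unintentional weight loss when BMI at enrollment is above 25 and puts no ceiling in its place

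*Protocol*

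**What the plan says.** Section 5.3 of the Protocol opens with "Patients eligible for this study must not meet any of the following criteria", so each item is a bar in its own right. Item 5 has two sentences.

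- The first excludes unintentional loss of 5% or more "in the last three months, unless the patient has a BMI" above 25 kg/m².
- That BMI is the one measured "at study enrollment. Intentional weight loss is permitted if" it is below 10% over three months and BMI is above 22 kg/m². The 10% figure is therefore attached to intentional loss only.

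Under Study Design and Treatment the diet is set out as follows: "On day 1, the total caloric content of the FMD is of about 700 KCal; on days 2-5, the caloric content is 300 KCal". Cohorts A and B receive one cycle, started within 15 days of surgery and finished at least 7 days before it. Cohort C receives four cycles at 28-day intervals.

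Several other entry criteria bear on nutritional risk without measuring recent weight loss:

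- Inclusion 6: "Presence of an Eastern Cooperative Oncology Group (ECOG) performance status 0 or 1".
- Inclusion 7: "Albumin > 3 g/dL".
- Exclusion 3: a BMI floor of 20.
- Exclusion 13: severe GI impairment or "GI disease that may alter the digestion and absorption of nutrients during the re-feeding phase".
- Exclusion 22: serious illness that, in the investigator's assessment, "renders the patient not suitable for participation in this clinical study".

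**The concern.** By writing item 5, the sponsor treats recent unintentional weight loss as relevant to whether this diet may be given. Allowing more loss in heavier patients is a legitimate choice. The difficulty is that the exception removes the limit altogether: a 6% loss and a 20% loss are treated alike, provided the patient still ends above BMI 25.

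This is a matter of eligibility and safety. The centre has no stated weight-loss ground for turning away a patient above BMI 25 who has unintentionally lost 10% or more in three months. The next step for that patient is severe short-term energy restriction, which in two of the three cohorts comes shortly before an operation.

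**Working it through.** The plan gives no figure of its own to reproduce here. The check is a reading of the criteria followed by simple arithmetic.

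**Inputs.** Exclusion 5: 5% limit, waiver above BMI 25 at enrollment, three-month window, 10% limit for intentional loss. Study Design and Treatment: energy content, number of cycles, timing relative to surgery. The earlier BMI values below are illustrations, because the document gives no BMI distribution.

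**1. Does any criterion cap unintentional loss above BMI 25?** The first sentence of item 5 does not apply there, and the second concerns intentional loss. The BMI floor of 20 cannot act above 25. ECOG status and albumin do not measure recent loss. The disease-specific exclusions need an identified condition. Exclusion 22 needs a serious illness and names no weight figure. So no criterion caps it.

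**2. Largest loss the waiver admits.** Enrollment BMI must exceed 25, so the loss must be below 1 - 25 / (BMI three months earlier).

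| BMI three months earlier | Formula | Admitted loss is below |
|---|---|---|
| 28 | 1 - 25/28 | 10.7% |
| 30 | 1 - 25/30 | 16.7% |
| 35 | 1 - 25/35 | 28.6% |

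Example: 30 × 0.85 = 25.5, so a 15% loss from BMI 30 passes item 5.

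**3. The same calculation from enrollment.** For a patient enrolled at BMI 25.1, earlier BMI = 25.1 / (1 - loss). Losses of 10%, 15% and 20% imply an earlier BMI of 27.9, 29.5 and 31.4. Item 5 admits all three.

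**4. Where a 10% ceiling would act.** A 10% loss lands exactly on BMI 25 from an earlier BMI of 25 / 0.90 = 27.8. At or below that value, a loss of 10% or more ends at or under 25 and the existing 5% limit already excludes it. The ceiling changes eligibility only above 27.8, and there it holds the admitted loss below 10%.

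**5. What the admitted patient would undergo.**

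- Energy per cycle: 700 + 4 × 300 = 1,900 kcal over 5 days, a mean of 1,900 / 5 = 380 kcal/day.
- Cohort C: 4 × 1,900 = 7,600 kcal over 4 × 5 = 20 diet days.
- Cohorts A and B: a start on day -15 puts the last diet day at -11. The latest allowed last diet day is -7, with a start on day -11. The last diet day therefore falls 7 to 11 days before surgery.

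**The case against.** The strongest reply is that this is a clear, deliberate rule rather than a mistake. Heavier patients have more reserve, and the populations are operable early-stage breast cancer, node-positive melanoma awaiting dissection, and resected melanoma. To be affected, a patient must have had a BMI above 27.8, lost at least 10% without trying, and still meet the ECOG, albumin, hemoglobin, potassium, calcium and fasting-glucose requirements. Exclusion 22 covers serious illness behind a large loss. The diet can be stopped for toxicity or at the investigators' discretion, and nutritional parameters and adverse events are followed. The document calls itself a synopsis, so operational nutritional assessment may sit elsewhere. Nor does anything in it show that 10% is the right safety threshold.

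Most of this stands. It makes affected patients rare and limits the weight of the point. It does not supply a ceiling: the entry criteria listed are indirect, stopping rules and follow-up act only after the diet has begun, and the eligibility list itself is given in full. The lack of a documented safety basis for 10% is a reason to let the sponsor choose the figure. It is not a reason to have none.

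Three stronger readings are tempting and are not supported.

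- A reader might picture a patient with uninvestigated wasting. The criterion says unintentional, and such loss can have a known and resolved cause.
- A reader might infer that above BMI 25 the protocol is stricter on deliberate than on unintentional loss. That follows only if the second sentence of item 5 governs all intentional loss. If it merely relaxes the 5% limit, it has nothing to act on above BMI 25, and the text nowhere says outright that intentional loss of 10% or more is excluded.
- A reader might infer that the endpoints are compromised. Nothing in the document shows that.

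**Conclusion.** The point holds as a gap in one eligibility rule. Above BMI 25 at enrollment, unintentional three-month loss has no upper limit, and this is true on every reading of item 5. The percentages in the table are arithmetic bounds and not expected patients. The document gives no frequency, and among the 100 planned patients few, if any, are likely to be affected. The conclusion assumes only that BMI is measured at enrollment, as the item states, and that the listed criteria are the complete entry rules. Severity: consider.

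**What to change.** Amend exclusion 5 so that it excludes (a) unintentional loss of 5% or more in the last three months unless BMI is above 25 at enrollment, and (b) unintentional loss of 10% or more in the last three months at any BMI. The 10% is taken from the criterion's own limit on intentional loss; the sponsor may justify a different ceiling. The rule on intentional loss needs no change.

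The cost is a one-line amendment and the loss of very few otherwise eligible patients, all with a BMI above 27.8 three months before enrollment.

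### In Cohorts A and B the primary contrast at 30 days after surgery can absorb the effect of adjuvant therapy, because no cohort definition, exclusion or sample rule separates it from the FMD effect

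*Protocol*

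**What the plan says.** **Exclusions.** The list opens with "Patients eligible for this study must not meet any of the following criteria", so its items decide who may enter. Item 1 is "Prior systemic treatment for breast cancer or melanoma". Item 21 is "Ongoing therapy with systemic corticosteroids, or systemic corticosteroid therapy ≤ 2 weeks before study enrollment". Neither says anything about treatment started after enrolment. The reasons for interrupting the FMD (Duration of the treatment) name neither.

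**Primary endpoint.** Under Objectives and corresponding endpoints there are two PBMC contrasts. The first: "Short-term modifications refer to changes assessed the day of FMD discontinuation compared to the day of FMD initiation". The second: "Long-term modifications refer to changes detected the day of surgery or 30 days after surgery compared to the day of FMD initiation".

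**Design.** The trial is a "Single-arm, monocentric, prospective study designed to estimate the immunomodulatory and metabolic effects induced by the FMD". Study Design and Treatment foresees matched controls for the Cohort B lymph-node cell suspensions, but none for PBMCs.

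**Who is enrolled.** The Hypothesis/Rationale section says that "cancer patients who are not candidate to other medical treatments represent an ideal context to assess the effects of the FMD without other confounding factors". In Study Design and Treatment only Cohort C (20 patients) must consist of people who are not candidates for adjuvant treatment. Cohort A (40 breast cancer patients) is restricted only as to systemic treatment before surgery, and "Patients with any breast cancer biology, including hormone receptor-positive, HER2-overexpressing and triple-negative cancers, will be included in the study". T1N1 tumours are also admitted. Cohort B (40 patients) is melanoma with an involved sentinel node and carries no adjuvant restriction.

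**The concern.** A single-arm before-and-after comparison attributes to the diet whatever changed between the two samples. That can be defended only if nothing else that acts on immune cells begins in between. The sponsor evidently shares this view: it excludes steroids and earlier systemic treatment, and it justifies the setting by the absence of confounding treatment.

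The protection does not reach the later primary sample. A Cohort A or B patient can satisfy every criterion, complete the diet, have surgery, start adjuvant therapy and then give the 30-day blood sample. The contrast as defined takes that sample as it is. Systemic anticancer drugs, radiotherapy and systemic steroids can all change lymphocyte, NK and myeloid populations, which are the endpoint itself. Steroids can also change glucose and insulin (secondary objectives 4 and 5).

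At stake is whether a long-term change in up to 80 of the 100 patients can be credited to the FMD.

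**Working it through.** **1. How far the late samples lie from the diet.** Inputs from Study Design and Treatment: a 5-day diet, started within 15 days of surgery and completed at least 7 days before it. Let surgery be day 0 and the start day −S.

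- The last diet day is −S + 4. Completion at least 7 days before surgery requires S − 4 ≥ 7, so S ≥ 11. With S ≤ 15, the start lies on day −15 to −11.
- From start to the 30-day sample is S + 30, which gives 11 + 30 = 41 to 15 + 30 = 45 days.
- From the last diet day to the 30-day sample is (S − 4) + 30, which gives 37 to 41 days.
- Cohort C, four cycles every 28 days: cycle 4 starts on day 1 + 3 × 28 = 85 and ends on day 89. The last sample is at 89 + 30 = day 119.

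**2. Which samples each kind of treatment can reach.**

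| Sample | Adjuvant therapy or radiotherapy | Systemic steroid started after enrolment |
|---|---|---|
| A/B, end of diet | No, it precedes surgery | Possible, but only the 5 diet days are exposed |
| A/B, day of surgery | No, adjuvant treatment follows surgery | Possible |
| A/B, 30 days after surgery | **Yes, during the 30 post-operative days** | Possible |
| C, up to day 119 | No, by cohort definition | Possible |

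The adjuvant problem is therefore confined to one sample type in two cohorts (40 + 40 = 80 patients), with an exposed window of at most 30 days.

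**3. What such exposure could do.** The protocol states no power or effect size for this contrast, so there is no figure to reproduce. As an illustration, take the planned two-sided 5% Wilcoxon signed-rank test with n = 40, normal paired changes with SD 1, and a true FMD effect of zero. Let a share f of patients carry a shift of d SD from another treatment. **Both f and d are assumptions; neither is in the protocol.** The mean bias is f × d.

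| f | d (SD) | Mean bias f × d (SD) | Rejection rate |
|---|---|---|---|
| 0 | – | 0 | about 5% |
| 10% | 1 | 0.1 | about 9% |
| 10% | 2 | 0.2 | about 14% |
| 20% | 1 | 0.2 | about 19–20% |
| 20% | 2 | 0.4 | about 39–40% |

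Fixing exactly 4 or 8 exposed patients, instead of drawing them at random, lowers these a little: about 7–8%, 11–12%, 18% and 37–38% in the same order.

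**4. Sections that do not fit together.**

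- *Rationale against cohort definitions.* The rationale describes patients who are not candidates for other medical treatment. The design imposes this, as to adjuvant treatment, only on Cohort C.
- *Objective against blood schedule.* The primary objective uses surgery-day and 30-day samples. For Cohorts A and B, Study Design and Treatment lists blood only before the FMD and at diet completion.
- *Objective against Cohort C.* Long-term change is dated from surgery, but Cohort C patients have had their surgery before they start the diet. Their late sample is dated from the end of cycle 4.

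**The case against.** **The text is a synopsis, and the SAP is not shown.** Concomitant-treatment logs and rules on analysable samples often stand in a fuller document. This is fair, and it means that nobody can say such samples will in fact be analysed as FMD effects. But the cohort definitions, the reach of the exclusions and the choice of a 30-day primary time point are protocol content, and they conflict with the stated rationale. The longitudinal models mentioned under Statistical methodology could take account of other treatments only if the dates are collected.

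**The problem is not trial-wide.** A reader might infer that all primary samples in all cohorts are exposed for the whole 41–45 or 119 days. The protocol does not support that. Cohort C excludes adjuvant candidates, Cohort A excludes systemic treatment before surgery, and the short-term and surgery-day samples precede any adjuvant therapy.

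**A steroid at anaesthesia is a weak example.** It falls 30 days before the 30-day sample, well outside the protocol's own 2-week interval. It could matter to a surgery-day sample, but only if blood is drawn afterwards, and the protocol does not give the time of the draw.

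**The error rates are hypothetical.** This stands. They describe one unadjusted test in a study with many indicators that disclaims upfront statistical properties. The Hommel adjustment, planned as a robustness check, would make single rejections rarer. It does not remove a systematic shift, because it addresses multiplicity and not confounding.

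**Dropping samples selects patients.** If HER2-positive, triple-negative or node-positive patients start adjuvant therapy early, their samples go first, and possibly more than a few. This also stands and shapes the fix.

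**Conclusion.** The point holds for the 30-day post-operative PBMC contrast in Cohorts A and B. Followed as written, it would credit to the FMD any effect of adjuvant systemic therapy or radiotherapy started in the 30 days after surgery, and the single-arm design has no means of separating the two. A smaller gap, for steroids only, applies to any late sample, including Cohort C up to about day 119.

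The size is unknown. It depends on how many patients start such treatment before the sample and how far it moves each cell subset, and the protocol gives neither. The 9% to 40% range rests on the assumed 10–20% exposure and 1–2 SD shifts; with no exposure the test keeps its 5%. The conclusion also assumes that the 30-day draw takes place, which the primary objective requires but the Cohort A/B blood schedule does not list.

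A reader might go further and conclude that the short-term FMD findings or the Cohort C results are confounded by adjuvant therapy. The timing and the Cohort C definition rule that out.

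**What to change.** 1. Record the start dates of systemic corticosteroids, systemic anticancer therapy and radiotherapy for every patient up to the last sample.
2. Base the FMD-effect analysis of the long-term contrast on samples taken before the first adjuvant dose or radiotherapy session and not within 2 weeks after a systemic corticosteroid. The 2 weeks are the protocol's own interval, carried forward to each sample.
3. Show the all-samples result beside it. Neither is sufficient alone: one may be confounded, the other selected.
4. Report how many samples are removed, by cohort and tumour subtype.
5. Reconcile the primary objective with the Cohort A/B blood schedule, state how long-term change is defined for Cohort C, and reconcile the rationale with the cohort definitions.

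The cost is a short treatment log, a few sentences in the protocol or SAP, and some precision in the long-term contrast. That loss may be more than trivial if adjuvant therapy often starts within 30 days. The short-term contrast would hardly be touched. Whether such treatment should be given is a clinical matter on which nothing is proposed here; only its recording and the handling of samples are addressed.
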